4.4 Data Collection and Management

Data Collection and Management: During study visits, a study nurse and/or a research assistant will collect demographic and clinical data for study use. Clinical data collected will include vital signs, medical history and examination, adverse events and other data as required. Data will be entered into REDCap EDC. A Study Analyst will review and clean study data regularly including performing quality assurance checks to ensure that there are not any aberrations in the data that require further clarification and/or changes to the study forms or database.

Variables to be collected will include basic demographic (e.g., age, education level, marital status) and clinical (e.g gravidity and parity, contraception use, pregnancy testing) variables as well as symptom review will be collected. Demographic and clinical characteristics will be used to describe the study population.

Study tools will include a baseline data collection and physical exam form; follow-up visit data collection forms (symptom and adherence evaluation and physical exam).

Data Storage: Study records will be accessible only to study staff. The records will be held lockable cabinets at the study sites. Electronic data collected will be entered in REDCap EDC. The link between personal identity and unique identifier (PID) will be kept separate from study records and will not be included in the analytic database. This linkage will be destroyed at the conclusion of the study. REDCap EDC is compliant with clinical trial data management requirements.

1102 4.5 Statistical Considerations and Data analysis

4.5.1 Sample Size: A sample size of n=12 patients is needed for the primary objective of pharmacokinetics evaluation. To allow for potential drop offs, up to n=16 patients will be enrolled to have a sample size of n=12 fully evaluable participants.

1106 1107

1108

1109

1110

Sample Size Justification: This is the first study to evaluate the PK disposition of artesunate after intravaginal administration and thus no prior data are available to base the sample size calculation. The proposed sample size is based on the standard number of patients evaluated in clinical PK studies, ^{72–75} and is adequate to perform pharmacokinetic plasma parameters of artesunate and DHA in order to meet the study's primary objective.

1111 1112 1113

Accrual: We anticipate enrolling 2 participants a week. Hence we expect to enroll 12-16 participants in 6-8 weeks (1.5-2 months).

1114 1115 1116

4.5.2 Data Analysis Plans

- 1117 **Primary Outcome:** Plasma concentration versus time curve (AUC) of dihydroartemisinin
- 1118 (DHA) following five consecutive days of self-administration of 200mg Artesunate vaginal
- inserts (pessaries) among healthy women in Kenya.
- 1120 Primary Endpoint: Mean DHA AUC (ng*hr/ml) with standard deviation on Day 5
- 1121 Statistical analysis: Mean DHA AUC will be compared to historical studies after IV, oral and
- rectal administration among adults following similar dosing. Results will be analyzed using the
- student's t-test for one-sample observation and a p-value of 0.05 will be considered statistically
- 1124 significant.

1125 1126

Secondary Outcomes

- 1127 1.Plasma AUC of Artesunate following 5-day self-administration of 200mg Artesunate vaginal
- inserts (pessaries)
- 1129 Endpoint: Mean artesunate AUC (ng*hr/ml) with standard deviation on Day 5
- 1130 Statistical analysis: Mean artesunate AUC (ng*hr/ml) will be compared to historical studies after
- 1131 IV, oral and rectal administration among adults following similar dosing. Results will be
- analyzed using the student's t-test for one-sample observation and a p-value of 0.05 considered
- statistically significant.

1134

- 2. Maximum concentration of Artesunate (Cmax) following 5-day self-administration of 200mg
- 1136 Artesunate vaginal inserts (pessaries)
- 1137 Endpoint: Mean artesunate Cmax (ng/ml) with standard deviation on Day 5
- 1138 Statistical analysis: Mean artesunate Cmax (ng/ml) will be compared to historical studies after
- 1139 IV, oral, and rectal administration among adults following similar dosing. Results will be
- analyzed using the student's t-test for one-sample observation, and a p-value of 0.05 considered
- statistically significant.

- 3. Maximum concentration of DHA (Cmax) following 5-day self-administration of 200mg
- 1144 Artesunate vaginal inserts (pessaries)
- 1145 Endpoint: Mean DHA Cmax (ng/ml) with standard deviation on Day 5
- 1146 Statistical analysis: Mean DHA Cmax (ng/ml) will be compared to historical studies after IV,
- oral and rectal administration among adults following similar dosing. Results will be analyzed

PI: [name] UNIVERSITY OF NORTH CAROLINA Version 1.0 April 25, 2023

- 1148 using the student's t-test for one-sample observation and a p-value of 0.05 considered statistically 1149 significant.
- 1151 4. Time to maximum concentration (Tmax) of Artesunate following 5-day self-administration of
- 1152 200mg Artesunate vaginal inserts (pessaries)
- 1153 Endpoint: Mean Artesunate Tmax (mins) with standard deviation on Day 5
- 1154 Statistical analysis: Mean artesunate Tmax (mins) will be compared to historical studies after IV,
- 1155 oral, and rectal administration among adults following similar dosing. Results will be analyzed
- 1156 using the Mann-Whitney U-test for nonparametric data, and a p-value of 0.05 considered
- 1157 statistically significant.
- 1159 5. Time to maximum concentration (Tmax) of DHA following 5-day self-administration of
- 1160 200mg Artesunate vaginal inserts (pessaries)
- 1161 Endpoint: Mean DHA Tmax (mins) with standard deviation on Day 5
- Statistical analysis: Mean DHA Tmax (mins) will be compared to historical studies after IV, oral 1162
- 1163 and rectal administration among adults following similar dosing. Results will be analyzed using
- 1164 the Mann-Whitney U-test for nonparametric data and a p-value of 0.05 considered statistically
- 1165 significant. 1166

1150

1158

- 1167 6. Artesunate half-life (t_{1/2}) following 5-day self-administration of 200mg Artesunate vaginal
- 1168 inserts (pessaries)
- 1169 Endpoint: Mean Artesunate half-life $(t_{1/2})$ (mins) with standard deviation on Day 5
- 1170 Statistical analysis: Mean Artesunate half-life $(t_{1/2})$ (mins) will be compared to historical studies
- 1171 after IV, oral and rectal administration among adults following similar dosing. Results will be
- analyzed using the Mann-Whitney U-test for nonparametric data and a p-value of 0.05 1172
- 1173 considered statistically significant.
- 1175 7. DHA half-life $(t_{1/2})$ following 5-day self-administration of 200mg Artesunate vaginal inserts
- 1176 (pessaries)

1174

1182

- 1177 Endpoint: Mean DHA half-life (mins) with standard deviation on Day 5
- 1178 Statistical analysis: Mean DHA half-life (t_{1/2}) (mins) will be compared to historical studies after
- 1179 IV, oral and rectal administration among adults following similar dosing. Results will be
- 1180 analyzed using the Mann-Whitney U-test for nonparametric data and a p-value of 0.05
- 1181 considered statistically significant.
- 1183 8. Apparent clearance of Artesunate (AS) following 5-day self-administration of 200mg
- 1184 Artesunate vaginal inserts (pessaries)
- Endpoint: Mean Artesunate clearance (L/Kg/hr) with standard deviation on Day 5 1185
- 1186 Statistical analysis: Mean Artesunate clearance (L/Kg/hr) will be compared to historical studies
- 1187 after IV, oral and rectal administration among adults following similar dosing. Results will be
- 1188 analyzed using the students t-test for one-sample observation and a p-value of 0.05 considered
- 1189 statistically significant.
- 1191 9. Apparent clearance of DHA following 5-day self-administration of 200mg Artesunate vaginal
- 1192 inserts (pessaries)
- 1193 Endpoint: Mean DHA clearance (L/Kg/hr) with standard deviation on Day 5

PI: [name] UNIVERSITY Version 1.0

- 1194 Statistical analysis: Mean DHA clearance (L/Kg/hr) will be compared to historical studies after
- 1195 IV, oral and rectal administration among adults following similar dosing. Results will be
- analyzed using the students t-test for one-sample observation and a p-value of 0.05 considered

statistically significant.

1198

- 1199 10. Volume of distribution of Artesunate (AS) following 5-day self-administration of 200mg 1200 Artesunate vaginal inserts (pessaries)
- 1201 Endpoint: Mean Artesunate volume of distribution (L/Kg) with standard deviation on Day 5
- 1202 Statistical analysis: Mean Artesunate volume of distribution (L/Kg) will be compared to
- 1203 historical studies after IV, oral and rectal administration among adults following similar dosing.
- Results will be analyzed using the students t-test for one-sample observation and a p-value of
- 1205 0.05 considered statistically significant.

1206

- 1207 11. Volume of distribution of DHA following 5-day self-administration of 200mg Artesunate vaginal inserts (pessaries)
- 1209 Endpoint: Mean DHA volume of distribution (L/Kg) with standard deviation on Day 5
- 1210 Statistical analysis: Mean DHA volume of distribution (L/Kg) will be compared to historical
- studies after IV, oral and rectal administration among adults following similar dosing. Results
- will be analyzed using the students t-test for one-sample observation and a p-value of 0.05
- 1213 considered statistically significant.

1214

- 1215 12. Safety of 5-day course of self-administrated 200mg Artesunate vaginal inserts (pessaries) 1216 among health women in Kenya
- 1217 Endpoint: Type, frequency, severity, and duration of reported and observed adverse events (AEs)
- using the U.S National Cancer Institute Common Terminology Criteria for Adverse Events, v5.0
- 1219 (CTCAE 5.0) and the Division of AIDS Female Genital Adverse Events Grading Table
- 1220 Statistical Analysis: The counts of adverse events for each participant will be tabulated by
- severity (grades 1-5). The proportion of participants with a severe AE (grade 3 or higher) will
- be reported along the exact (Clopper-Pearson) one-sided upper 95% confidence bounds. The
- proportion of participants who report a severe AE (if any) will also be reported, along with an exact one-sided upper 95% confidence bound.

1225 1226 1227 - The at-risk period for safety will begin at study visit 1 (first artesunate use) and will continue through study visit 6 (4-10 days after last artesunate use). Safety data will be reported for all participants who start artesunate use.

- Pharmacokinetic analysis: Conventional pharmacokinetic parameters AUC (0, infinity), halflife, apparent clearance, volume of distribution, maximum plasma concentration (Cmax), time to
- 1232 Cmax will be determined from the plasma concentration-time data using noncompartmental
- analysis. 35,76 Peak plasma concentration (Cmax) and time to reach peak concentration (Tmax) for
- artesunate and DHA will be the observed values. The AUC of AS will be calculated by linear
- trapezoidal summation with extrapolation to infinity, and AUC time curve will start from drug
- administration to the last quantifiable observation. All parameters will be calculated using time
- in hours after the first drug administration. With respect to DHA, AUC will be calculated to the
- last drug measurable time point. The elimination rate constant (beta) will be calculated from the
- slope of the terminal phase of the log concentration-time profile, and the elimination half-life

- 1240 (t1/2) calculated from the ratio of ln 2/beta. Other PK parameters will be calculated using
- standard model-independent formulae.³⁹ The estimates of PK parameters for DHA will assume
- 1242 complete conversion of AS to DHA as reported previously.³⁵ Data will be plotted graphically
- and analyzed using statistical software. Data will be presented as mean with standard deviation
- 1244 (SD).
- 1245 **4.6 Community Engagement Plan**
- 1246 The target population will be sensitized about the study through talks in public forums including
- health facilities within Kisumu County where the study will be done.
- 1248 4.7 Study Limitations, Risks and Mitigation of Risks
- 1249 The study will investigate the pharmacokinetics of artesunate following intravaginal use at the
- proposed dosing and frequency. Limitations include not evaluating pharmacodynamics or
- pharmacokinetics following different dosing. Risks of the study and mitigation of risks are
- 1252 discussed under Ethical Considerations.
- 1253 4.8 Plans for Communicating Study Findings
- 1254 This study will provide important pharmacokinetics data to inform questions of serum levels if
- any following intravaginal artesunate use and implications for malaria resistance in endemic
- 1256 communities. The final study results will be shared with the study team, the study participants in
- lay language, the medical and scientific communities including all stakeholders, and the public.
- Results will be published in peer reviewed scientific journals, abstracts, posters and symposium
- presentations at conferences. Results will also be shared with relevant stakeholders including the
- 1260 Ministry of Health in Kenya.
- 1261
- 1262 5 ETHICAL CONSIDERATIONS
- 1263 All investigators and study staff will undergo online Good Clinical Practice (GCP) and Human
- Participants Protection (HSP) training to ensure high levels of adherence to ethical principles of
- 1265 clinical research. They will also be expected to meet basic professional training based on their
- 1266 roles and functions.
- 1267 5.1 Institutional Review Board (IRB) Approval and Consent
- This study will be reviewed and approved by the IRB at the University of North Carolina (UNC),
- as well as all relevant regulatory bodies in Kenya, which include the Amref Ethics and Scientific
- 1270 Review Committee (ESRC), the Kenya Pharmacy and Poisons Board (PPB), the National
- 1271 Commission for Science, Technology & Innovation (NACOSTI) and any other regulatory bodies
- required in-country.
- 1273
- 1274 The Amref ESRC & UNC IRB's will have the proper representation and function in accordance
- with federally mandated regulations. The IRB will approve the informed consent form (ICF),
- study protocol, any other written information to be provided to participants and other study
- 1277 related documents as per the ethics and regulatory submission requirements. All amendments
- 1278 (e.g., those that affect the conduct of the study or the safety of participants) will require
- approval from all regulatory bodies. Before the investigational product can be shipped to the
- investigational site, a shipping permit will be obtained from the Pharmacy and Poisons board.

CONFIDENTIAL

PI: [name] UNIVERSITY OF NORTH CAROLINA April 25, 2023 Version 1.0

1282 In obtaining and documenting informed consent, the investigator will comply with the applicable 1283 regulatory requirement(s) and should adhere to Good Clinical Practice (GCP) and to ethical 1284 principles that have their origin in the Declaration of Helsinki.

1285 1286

1287

1288

1289

1290 1291

1292

1293

1294

1295

1296

1297

1298

1299

1300

1301

1302

1303

1304

Before recruitment and enrollment onto this study, the patient will be given a full explanation of the study, including the goals of the study, the risks and benefits and will be given the opportunity to review the consent form. As part of informed consent, the voluntary nature of study participation will be emphasized to potential participants, including the fact that their participation, or non-participation in the study will not impact their ongoing or future care. Each consent form must include all the relevant elements currently required by the and local or state regulations. Once this essential information has been provided to the patient and the investigator is assured that the patient understands the implications of participating in the study, the patient will be asked to give consent to participate in the study by signing an IRB-approved consent form. The written informed consent form will be signed and personally dated by the patient and by the person who conducted the informed consent discussion. Informed consent will be obtained from all participants in their preferred languages. To compensate for participants time, including potential lost wages from time spent on study visits, each scheduled study visit will be reimbursed Kshs 1000 (approximately \$10). Additionally, participants will be reimbursed for transport, taking into consideration average cost of travel to the clinic to support follow-up and retention, expected at approximately Kshs 500 (\$5). On Visit # 5 when participants are expected to spend 6-8 hours in the study clinic, participants will be reimbursed an additional Kshs 2,500 (US \$25) for lost wages. During study visits, participants may receive a meal or refreshment based on their waiting time.

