Pharmacokinetic analysis: Conventional pharmacokinetic parameters - AUC (0, infinity), half-life, apparent clearance, the volume of distribution, maximum plasma concentration (Cmax), time to Cmax will be determined from the plasma concentration-time data using noncompartmental analysis. Peak plasma concentration (Cmax) and time to reach peak concentration (tmax) for artesunate and DHA will be the observed values. The AUC of AS will be calculated by linear trapezoidal summation with extrapolation to infinity. With respect to

DHA, AUC will be calculated to the last drug measurable time point. The elimination rate constant (β), will be calculated from the slope of the terminal phase of the log concentration-time profile, and the elimination half-life (t1/2) calculated from the ratio of ln 2/ β . Other PK parameters will be calculated using standard model-independent formulae.³⁹ The estimates of PK parameters for DHA will assume complete conversion of AS to DHA as reported previously.³⁵ Data will be plotted graphically and analyzed using statistical software. Data will be presented as mean with standard deviation (SD).

Compliance Statement: Biospecimen collection for this study will be conducted in full accordance with all applicable University of North Carolina (UNC) Research Policies and Procedures including Good Clinical Practice (CGP) policies, and all applicable Federal and state laws and regulations including 45 CFR 46, and the Health Insurance Portability and Accountability Act Privacy Rule, as well as the in-country regulatory agencies including the Amref Ethics and Scientific Review Committee (ESRC), the Kenya Pharmacy and Poisons Board (PPB), the National Commission for Science, Technology & Innovation (NACOSTI) and any other regulatory bodies required in-country. Any episode of noncompliance will be documented. The investigators will perform the study in accordance with this protocol, will obtain consent, and will report unexpected problems in accordance with the UNC IRB Policies and Procedures and all federal requirements. Collection, recording, and reporting of data will be accurate and will ensure the privacy, health, and welfare of research participants during and after the study.

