Risk of developing artemisinin resistance for malaria treatment: As discussed in section 3.1, the dosing used for intravaginal use is much lower than that used for the rectal artesunate formulation for malaria treatment. Compared to the rectum, vascularity at the vaginal and cervix is significantly less hence likelihood of systemic exposure is exceedingly low. As such, minimal to no appreciable levels of the active substance are expected following intravaginal use of artesunate at the planned dosing and frequency. The objective of this study is to confirm this.

1343 1344 1345

1346

1347

1348

1349

1350

1351

1352

1353

Risk of breach of confidentiality: Other small risks associated with study participation include a risk of breach of confidentiality during the study. This will be minimized through using only a unique participant identification number, and not participant names or other identifiers. Study participation will include data collection regarding basic medical history. The risk of this is minimal as questions asked will be routine medical questions. However, all efforts will be made to reduce the risk of distress to participants including using experienced interviewers, offering interviews in privacy for all participants, and reviewing the confidentiality of all answers at the beginning of data collection. Study staff will monitor participants for any signs of psychological distress and refer participants for additional counselling, as needed.

1354 1355

1358

1359

1360

1361

1362

1363

1364

1365

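### The AUC and Cmax analyses concern group means, while the stated question is whether a user reaches appreciable blood levels; no planned conclusion rests on individual women

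*Combined protocol and SAP*

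**What the plan says.** Section 4.5.2 defines the primary endpoint as "Primary Endpoint: Mean DHA AUC (ng*hr/ml) with standard deviation on Day 5". It is to be compared with historical values after IV, oral and rectal dosing in adults, by "student's t-test for one-sample observation and a p-value of 0.05 will be considered statistically" significant. Artesunate AUC, both Cmax endpoints, and clearance and volume for both analytes follow the same pattern. That makes 8 of the 12 PK endpoints. The other four, Tmax and half-life, are also worded as means but are analysed "using the Mann-Whitney U-test for nonparametric data, and a p-value of 0.05 considered" significant.

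The pharmacokinetic paragraphs of sections 4.4 and 4.5.2 both say: "Data will be presented as mean with standard deviation". They also promise plots, and the synopsis says that parameters are calculated for each participant. No median, range, maximum, individual listing or count of women with quantifiable drug is planned. The only per-participant proportion is for severe adverse events, with an exact Clopper-Pearson one-sided upper 95% bound.

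On the aim, the resistance paragraph of section 5.4 expects negligible levels after vaginal use and adds: "The objective of this study is to confirm this". The Lay Summary puts the question for a woman who uses the pessary for five days: can the drug be found in her blood? On size, section 4.5.1 says: "A sample size of n=12 patients is needed for the primary objective of pharmacokinetics evaluation". It gives no effect size, SD or power.

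**The concern.** Sections 5.4 and IV describe what happens in a user. The AUC and Cmax tests describe the average of 12 users. The two can disagree: if most women absorb almost nothing and a few absorb as much as by the rectal route, the mean falls well below the rectal value and the test is significant, although some users have the exposure that the trial is meant to rule out.

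What is at stake is the inference from the main result. A report that vaginal exposure differs significantly from oral, rectal or IV exposure could be taken as support for the section 5.4 expectation when the same data contradict it for some women.

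**Working it through.** **The plan's own figure.** The 12 evaluable women cannot be re-derived, because section 4.5.1 rests on custom. The check is therefore on what the planned test would say.

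**Inputs from section 1.3.** DHA AUC in healthy adults: rectal 200 mg, 965 ng·h/ml; oral 200 mg, 1158 to 1331; IV 120 mg, 1850. These are treated as fixed. The plan does not state sidedness; I use two-sided 0.05.

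**Step 1: a split sample against the rectal value.** Assume k of 12 women at A = 965 and the rest at 0.
- Mean = kA/12
- SD = A × √[k(12 − k)/(12 × 11)]
- t = (mean − A)/(SD/√12) = −√[11(12 − k)/k], 11 degrees of freedom

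For k = 5: mean = 5 × 965/12 = 402; SD = 965 × √(35/132) = 497; standard error = 497/√12 = 143.5; t = (402 − 965)/143.5 = −3.92; p = 0.0024.

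| Women at 965 | Mean | SD | p against 965 |
|---|---|---|---|
| 1 | 80 | 279 | 2.8 × 10⁻⁷ |
| 3 | 241 | 436 | 0.00013 |
| 4 | 322 | 475 | 0.0007 |
| 5 | 402 | 497 | 0.0024 |

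Against 1158, 1331 or 1850 the p-values are smaller still. If the absorbers instead sit at 1331, the test against 965 stays significant up to k = 4 (p at most 0.025) but not at k = 5 (p 0.062 to 0.081, with the others at 0 to 100).

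**Step 2: with variation between women.** Assume lognormal values, absorbers averaging 965 and the others 50.
- 4 absorbers of 12: mean significantly below 965 in 99.5%, 93.4% and 87.0% of simulated trials at CV 30%, 50% and 70%.
- Random 20% share, CV 30% to 50%: significant in 99.5% to 97.0% of trials. Random 30% share: 97.2% to 91.5%.

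**Step 3: the hypothesis in section 2.1.** This is no difference from baseline, for which section 4.5.2 names no test. If it were tested on means with non-absorbers at 0, t = √[11k/(12 − k)], giving p = 0.34, 0.17 and 0.08 for k = 1, 2 and 3. It would be retained with three full absorbers.

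**Step 4: what a count of women can say.** The exact one-sided 95% upper bound for 0 of 12 is 1 − 0.05^(1/12) = 22.1%; for 1 of 12 it is 33.9% and for 2 of 12 it is 43.8%. At a true share of 20%, at least one such woman is among the 12 with probability 1 − 0.8¹² = 93%. Bounding the share below 10% with none seen would need 29 women, since 0.9²⁹ = 0.047 and 0.9²⁸ = 0.052.

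**Step 5: a tempting alternative.** A log-scale upper prediction limit for one further woman is the geometric mean × exp(1.87 × SD of logs), where 1.87 = 1.796 × √(13/12). It assumes a single lognormal population. In the Step 2 mixture, among trials containing at least one full absorber, it falls below 965 in about 51% to 52% (20% share) and about 25% (30% share).

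**The case against.** The best defence is that the trial is descriptive. Section 2.2 sets out only to determine the AUC, and the sentence about confirming negligible levels stands in the ethics section. Nothing in section 4.5.2 says that a mean below the oral or rectal value will be read as absence of appreciable exposure. This stands in part: the mismatch is between the analysis and the claims in section 5.4 and the Lay Summary, not with section 2.2. The section 5.4 sentence is nevertheless a statement of the study's objective, and no planned result serves it.

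The second defence is that a split would be visible. The SD is part of the endpoint and the data are plotted. In the mixture above, the SD exceeds the mean in about 92% to 99% of trials that contain a full absorber, an obvious warning for a non-negative quantity. This also stands, so it would be wrong to infer that absorbers would be concealed. No planned rule or conclusion acts on that warning.

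Third, no document points to a subgroup that absorbs fully. Sections 1.6 and 2.5 argue on anatomy for low absorption. This is correct: the split is an assumption used to test the method, not a prediction.

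Fourth, a count of women with any quantifiable drug does not separate traces from full absorption, and the plan defines no appreciable level. This is also fair, and is why the individual values must accompany the count.

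**Conclusion.** The point holds for AUC and Cmax. Their analyses concern group means and cannot support a conclusion about what a user's blood level will be. Under an assumed all-or-nothing split, the primary test remains significant against the rectal value with 5 of 12 women at full rectal exposure (p = 0.0024). With 20% to 30% absorbers and CV 30% to 50%, it is significant in about 92% to 99.5% of trials. The absorber share, the low AUC values and the CVs are assumptions, and the historical means are taken as exact.

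Two stronger readings are not supported. A reader might infer that every planned PK test is a test on a mean, but Tmax and half-life use a rank test (neither measures the amount of exposure). A reader might also infer that the plan will declare vaginal exposure significantly lower as its success criterion. Section 4.5.2 speaks only of statistical significance, and the expectation of a significantly lower level is stated in section 2.5, for the maximum concentration only.

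This is a worthwhile and inexpensive change to the analysis. It is not a flaw in the design or the sampling.

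**What to change.** Amend section 4.5.2, and the matching paragraph in section 4.4, before assay results are seen:

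- Keep mean and SD as descriptive summaries, and state that the section 5.4 conclusion will rest on individual women.
- List each woman's Day 5 AUC and Cmax for DHA and artesunate, with median, range and maximum.
- In all cases, whatever the data look like, report the number of women with any quantifiable post-dose DHA or artesunate, with the exact one-sided 95% upper bound already specified for severe adverse events.
- State in advance that 0 of 12 gives an upper bound of 22.1%, so 12 women cannot exclude a 20% share of absorbers.
- Do not base the conclusion on a lognormal prediction limit, for the reason in Step 5.

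The cost is some wording and one table, with no new samples or participants. The downside is a less favourable statement than the test on the mean would give.
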